- **E-learning platform:** Module content will first be disseminated to practice site personnel via an online e-learning platform (i.e., Articulate). Study coordinators will obtain e-mail addresses for the site personnel from either the health system liaison or the associated vaccine champion, and will then e-mail a training content link to all appropriate site providers, nurses, and staff. Attached to this initial e-mail will be an Information Sheet describing the study goals and training phase details, as well as their involvement throughout the duration of the 12-month QI intervention (see “*TrainingPhaseEmail...*” and “*InformationSheetTrainingPhase...*” documents; also see “Consent Process” section for more detail). After reviewing the Information Sheet and discussing any questions/concerns with study staff, site personnel will be asked to access and complete the training lessons prior to their scheduled site meeting.

Embedded at the conclusion of the online training module, will be a link to a brief REDCap survey (see “*TrainingModuleCompletionSurvey...*” document) to obtain information regarding those who have fully completed the training. A list of practice personnel who have successfully completed the online training will be stored in a password-protected Excel/Word file by each study coordinator. The names will not be linked with any other study data. The list will be accessible only by study staff for the purposes of confirming those who should receive CME/CNE credit.

Note: For intervention sites that have completed the e-learning training during the first half of the calendar year (i.e., prior to July), site personnel may be asked to additionally complete an abbreviated “flu booster” e-learning module just prior to flu season of that same year (e.g., in Aug/Sept). This abbreviated version (approx. 15 minutes to complete) will contain content (see table 3) only applicable to influenza.

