### Final Time/Cost Analysis:

Upon completion of aim/phase 2 we will conduct a final time/cost analysis. Our two-fold cost measures are (a) total intervention cost to implement the VAX-MOM program aggregated at the four health-system level under a cost analysis and (b) cost per additional flu or Tdap vaccination under a subsequent cost-effectiveness analysis. To derive a policy implication regarding the sustainability of programs, we will estimate costs and ICER estimates from the health system perspective.

**Total Cost:** To make these cost measures comparable to similar past interventions of reminders and educational programs, we will estimate cost with one-year time horizon, excluding the cost to purchase, store and administer vaccines. We will estimate the total intervention cost, summing non-personnel costs (e.g., EHR hardware, software, and materials) and personnel costs. The personnel costs will distinguish research costs from intervention costs (e.g., practice-level meeting and collecting EHR data). The dollar values of these personal costs will be calculated by multiplying “time efforts” (weekly reported by study personnel using a REDCap email survey) with the nationally representative “hourly-wage rates” by occupation codes of study personnel, derived from the Bureau of Labor Statistics.

**Cost-Effectiveness:** We will develop a standard decision model for our cost-effectiveness analyses. The effectiveness measures are the rates of flu and Tdap vaccination estimated under Aim 2b.

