As explained above, this intervention cost will exclude the cost to purchase, store and administer vaccines, which is assumed to be identical among all practices. Applying the same assumption, the average cost for the control group (costControl) is zero. To make separate ICER estimates for flu and Tdap vaccination, the Tdap-vaccination-specific costStudy will be estimated during non-flu season (April to September) first and applied for calculating the flu-vaccination-specific costStudy during a flu season (October to March), assuming the Tdap-vaccination-specific costStudy is constant throughout a year. Using the developed standard decision model, we will conduct probabilistic analyses to generate point estimates and 95% CIs for ICERs and one-way sensitivity analyses to determine conditions for being lower than the thresholds of cost-effectiveness, e.g., healthcare-system based quality improvement interventions to improve flu vaccination uptake targeting general populations (median ICER \$51 among 23 interventions) and healthcare workers (median ICER \$125 among 6 interventions) reported by a systematic review.

Hyp. : Cost per additional flu or Tdap vaccination under the VAX-MOM is lower than past similar interventions.

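### The seasonal split of programme cost assumes a constant Tdap cost, so the vaccine-specific ICERs depend partly on when sites were trained

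*Combined protocol and SAP*

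**What the plan says.** Section 17, Final Time/Cost Analysis, plans a total intervention cost and then a cost per additional flu or Tdap vaccination. Total cost is built by "summing non-personnel costs (e.g., EHR hardware, software, and materials) and personnel costs", and "we will estimate cost with one-year time horizon". Because "the average cost for the control group (costControl) is zero", the ICER numerator is the intervention-arm cost itself.

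For separate ICERs, "the Tdap-vaccination-specific costStudy will be estimated during non-flu season (April to September) first" and is then "applied for calculating the flu-vaccination-specific costStudy during a flu season (October to March"), "assuming the Tdap-vaccination-specific costStudy is constant throughout a year". The section gives no equation and no rule for annualising one-off cost or sharing joint cost. The sensitivity analyses it names are one-way analyses against cost-effectiveness thresholds; none varies the allocation.

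Section 4, Step 1, describes training given first by e-learning and then at a site meeting, with content on both vaccines (Table 3). The E-learning platform note begins "For intervention sites that have completed the e-learning training during the first half of the calendar year (i.e., prior to July") and says that such sites may be given a short flu-only module in August or September. The Site Meeting note makes the same provision for a flu-only meeting. In Step 2, rate feedback recurs every other month and PDSA cycles recur monthly.

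**The concern.** A seasonal split by remainder works if everything except the flu-specific work costs the same in both half-years. Up-front training breaks that condition. Its cost arises once, covers both vaccines, and falls in whichever half-year a site happened to be trained. If it falls in April to September, the rule reads it as Tdap cost, assumes that it recurs in the second half-year, and deducts it again when forming the flu cost. If it falls in October to March, the rule gives all of it to flu.

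The flu-only booster shows the fault most plainly. It is spending on flu alone, scheduled inside the window from which the Tdap cost is estimated.

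At stake are the two vaccine-specific ICERs and the Section 17 hypothesis that cost per additional flu or Tdap vaccination is lower than in past interventions, for which median benchmarks of $51 and $125 are cited. With control cost set to zero, any misallocation passes straight into the numerator.

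**Working it through.** The plan states no vaccine-specific cost or ICER, so there is no figure to reproduce. The check is the algebra of the rule, followed by an illustration with assumed dollars.

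**Inputs from the documents:** two six-month windows, Tdap cost held constant across them, control cost zero, and up-front training on both vaccines.

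**Notation:** S is one-off cost, s the share of S incurred in April to September across the programme, r the recurring shared cost per month, and f the extra cost per flu-season month.

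**Split, with flu as the remainder:**

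- April to September cost: N = 6r + sS
- October to March cost: F = 6r + 6f + (1-s)S
- Tdap for the year: 2N = 12r + 2sS
- Flu: F - N = 6f + (1-2s)S
- Check: 2N + (F - N) = 12r + 6f + S, the true total

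At s = 0 all of S goes to flu. At s = 0.5 it cancels from flu and all of it goes to Tdap. At s = 1 it is charged twice to Tdap and deducted once from flu. Flu cost is negative only if (2s-1)S > 6f.

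**Booster:** a flu-only booster costing B in August or September raises N by B. Tdap therefore rises by 2B and flu falls by B. The net is B, as it should be, but on the wrong vaccine.

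**Illustration (assumed: S = $2,000, r = $150, f = $100):**

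| s | Flu = 600 + (1-2s)2,000 | Tdap = 1,800 + 4,000s | Total |
|---|---|---|---|
| 0 | $2,600 | $1,800 | $4,400 |
| 0.5 | $600 | $3,800 | $4,400 |
| 1 | -$1,400 | $5,800 | $4,400 |

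**Range over other assumed values (r = $1,000, f from $0 to $1,000, S from $2,000 to $10,000):** flu is $2,000 to $16,000 at s = 0, $0 to $6,000 at s = 0.5, and -$10,000 to $4,000 at s = 1.

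**Effect on the ICER (illustration only):** take the design difference of 6.3 points and read the Section 17 sample size as 5,000 women in 16 practices per arm. Additional vaccinations per practice are then 0.063 x 5,000 / 16 = 19.7. Treating the dollar amounts in the table as per practice, the flu ICER is about $132, $30 or -$71 for s = 0, 0.5 or 1. The first exceeds both benchmarks and the second is below both. If 5,000 is the total for both arms, the denominator halves and the figures double to about $264, $61 and -$142.

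**The case against.** The strongest reply is that the subtraction is inferred. Section 17 does not use the word, prints no equation, and does not say that every dollar spent in April to September is Tdap cost. That is true, and the algebra above is conditional on the reading. But the text does state a rule: estimate in one window, hold constant, apply in the other. Some form of remainder is the natural way to carry it out.

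Second, the timeline (Figure 2) and the two time-and-cost surveys were not available for this check. Training dates cannot be confirmed, the booster is optional, and the surveys may already itemise training. This stands: s is unknown and a tag may already exist. It does not supply an allocation rule, which Section 17 lacks. That section does count practice-level meetings as intervention cost: "The personnel costs will distinguish research costs from intervention costs (e.g., practice-level meeting and collecting EHR data").

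Third, a reader might infer a swing of 2S at every site. That is only the gap between the two extremes. Total cost is to be aggregated across the four health systems and no site-level ICER is planned, so mixed training dates pull s towards the middle. At s = 0.5 the training term leaves the flu cost, but all of it then sits on Tdap, so mixing does not produce a fair split.

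Fourth, a reader might infer that EHR set-up is a known one-off item. Section 17 lists EHR hardware and software without timing, and report building recurs. Only the training is clearly up front.

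**Conclusion.** The concern holds as a fault in the allocation rule. On the natural reading, the division of cost between flu and Tdap depends partly on training dates rather than on resources used, and flu-only booster spending lowers the apparent flu cost. The flu distortion from training is (1-2s)S at programme level. Its dollar size cannot be fixed from the documents, which give no cost amounts; every dollar figure above is an assumption.

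A stronger reading would be that the plan will yield a negative flu cost that then counts as passing any threshold. The documents do not support that. A negative value needs (2s-1)S > 6f, which cannot be checked, and Section 17 does not say how such a value would be handled. Nor does the hypothesis clearly require both vaccines to beat past interventions; it is worded as one or the other.

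The scope is the vaccine-specific ICERs and their comparison with past interventions. Total cost is preserved under any s, and the primary vaccination analysis is untouched. The point should be corrected, but it does not threaten the trial's main result.

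**What to change.** Amend the Cost-Effectiveness text in Section 17 as follows:

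- State the allocation formula.
- Separate one-off training and set-up cost from recurring cost, and apply the seasonal step to recurring cost only.
- Charge flu-only boosters directly to flu.
- Allocate shared one-off cost by a pre-stated share, for example 50:50, varied from 25:75 to 75:25 in sensitivity analysis.
- Report one combined ICER, total cost divided by additional flu plus Tdap vaccinations, which needs no split.

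In the $4,400 illustration, 50:50 gives flu 600 + 1,000 = $1,600 and Tdap 1,800 + 1,000 = $2,800 whatever the training date. Giving flu 25% or 75% of S moves the flu cost to $1,100 or $2,100.

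The cost is SAP wording, plus a one-off/recurring tag in the two time-and-cost surveys if they do not already carry one. The downside is that the share is a convention, which the sensitivity range makes visible. Recurring shared cost would still fall on Tdap under the seasonal step, which is a further reason to report the combined ICER.
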